9.4.3.2.2. Comparative Tolerability

Comparative tolerability, as assessed by the FACT-GP5, is also a key secondary endpoint and will be tested conditionally on achieving a statistical significance for PFS and TFFS by BICR. Comparative tolerability will be defined as a comparison of the proportion of time on treatment with a high symptom burden as assessed by FACT-GP5 between Arm A and Arm B. A detailed analytical approach will be provided in the SAP.

Comparative tolerability will be assessed in the Tolerability Evaluable Population, i.e., patients enrolled by the time of the interim analysis (approximately 250 patients projected to be enrolled) regardless of the sample size re-estimation result. Since the sample size is fixed for the comparative tolerability endpoint, no adjustment of test statistic will be applied, and the type I error will not be inflated by a potential sample size increase.

9.4.3.2.3. Overall Survival

The study is not powered for OS but will continue to approximately 125 OS events or until a maximum of 6 years from the first patient visit, whichever comes first. If the true OS HR is 0.7, 125 OS events will provide approximately 98% probability that the observed OS HR would be less than 1.0, indicating no OS detriment associated with the selpercatinib treatment. A HR of 0.7 translates into a 42.9% relative and 30 months absolute increase in median OS (if assuming a median OS of 70 months for cabozantinib/vandetanib and 100 months for selpercatinib).

Overall survival (OS) is defined as the time from randomization until death from any cause. If the patient is alive or lost to follow-up at the time of data analysis, OS data will be censored on the last date the patient is known to be alive. Overall survival will be compared between treatment arms using a stratified log-rank test, stratified by the randomization strata for *RET* mutation (M918T vs. other) and intended treatment (cabozantinib vs. vandetanib). The

corresponding HR between treatment arms will be estimated using a stratified Cox regression model (Cox 1972), stratified by the randomization strata. Overall survival curves, the median and survival rates at various time points with 95% CI, for each treatment arm will be estimated using the Kaplan-Meier method (Kaplan and Meier 1958). Sensitivity analyses for OS will be described in the SAP.

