4.1. Overall Design

This is a global, multicenter, randomized (2:1), open-label, Phase 3 study comparing selpercatinib (treatment Arm A) to physician's choice of cabozantinib or vandetanib (treatment Arm B) in patients with progressive, advanced, kinase inhibitor naïve, *RET*-mutant MTC.

Patients will be randomized in a 2:1 ratio to selpercatinib or physician's choice of cabozantinib or vandetanib.

Patients will be stratified based on:

- *RET* mutation: M918T vs. other
- Intended treatment if randomized to control arm: cabozantinib vs. vandetanib.

Approximately 250 patients will be initially enrolled to the study. A sample size re-estimation based on comparative data will be conducted at the interim efficacy analysis. The total number of patients could be increased from the initially planned 250 up to a maximum of approximately 400 depending on the results of the interim efficacy analysis.

Patients with histologically confirmed, unresectable, locally advanced or metastatic MTC who have not received previous treatment with a kinase inhibitor are eligible for enrollment in this study. Patients are required to have radiologic progressive disease per RECIST 1.1 at screening compared with an image obtained within the prior 14 months. Patients are also required to have a documented *RET* mutation (Appendix 6) in tumor or germline DNA identified through molecular assays. The *RET* result should be generated from a laboratory with certification by Clinical Laboratory Improvement Amendments (CLIA), International Organization for Standardization/Independent Ethics Committee (ISO/IEC), College of American Pathologists (CAP), or other similar certification. In regions or at sites where *RET* is not standard of care and/or an acceptable local test (as defined by Lilly) is not available, a pre-screening consent will be used to provide the patient with a sponsor-supported testing option to determine tumor *RET* status. In addition, the sponsor or its designee will review all imaging to confirm progressive disease per RECIST 1.1 in the prior 14 months and all molecular pathology reports to confirm the presence of a valid *RET* alteration prior to enrollment.

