The ORR and DCR, with 95% CI, will be summarized for each treatment arm. Overall response rate and DCR will be compared between Arm A and Arm B using a Cochran-Mantel-Haenszel (CMH) test stratified by the randomization strata. The ORR and DCR according to both BICR and investigator-assessed BOR will be evaluated.

Maximum change in tumor size is defined as the ratio of best postbaseline tumor size over that of baseline. The maximum reduction from baseline in the sum of target lesions (based on investigator assessment) will be presented per patient in a waterfall plot.

Duration of response (DOR) is defined as the time from the date that measurement criteria for CR or PR (whichever is first recorded) are first met until the first date that disease is recurrent or documented disease progression is observed, per RECIST 1.1 criteria, or the date of death from any cause in the absence of documented disease progression or recurrence. The DOR according to both BICR and investigator-assessed BOR will be evaluated. The DOR will be analyzed for patients who achieve a BOR of CR or PR.

Duration of response will be compared between treatment arms using a stratified logrank test, stratified by the randomization strata. The corresponding HR between treatment arms will be estimated using a stratified Cox regression model (Cox 1972), stratified by the randomization strata. Survival curves, the median and rates at various time points with 95% CI, for each treatment arm will be estimated using the Kaplan-Meier method (Kaplan and Meier 1958).

Overall Survival

Overall survival (OS) is defined as the time from randomization until death from any cause. If the patient is alive or lost to follow-up at the time of data analysis, OS data will be censored on the last date the patient is known to be alive.

The study is not powered for OS but will continue to approximately 125 OS events or until a maximum of 6 years from the first patient visit, whichever comes first. If the true OS HR is 0.7, 125 OS events will provide approximately 98% probability that the observed OS HR would be less than 1.0, indicating no OS detriment associated with the selpercatinib treatment. A HR of 0.7 translates into a 42.9% relative and 30 months absolute increase in median OS (if assuming a median OS of 70 months for cabozantinib/vandetanib and 100 months for selpercatinib).

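### An observed OS hazard ratio below 1.0 is read as showing no detriment, but a point estimate below 1 does not exclude harm

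*Protocol*

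**What the plan says.** Protocol 9.4.3.2.3 opens with "The study is not powered for OS" and says that follow-up "will continue to approximately 125 OS events or until a maximum of 6 years from the first patient visit, whichever comes first". It continues: "If the true OS HR is 0.7, 125 OS events will provide approximately 98% probability" that the observed HR falls below 1.0, and glosses that outcome as "indicating no OS detriment associated with the selpercatinib treatment". SAP 8.4.2 repeats the statement: "125 OS events will provide approximately 98% probability that the observed OS HR would be less than 1.0", with the same gloss. The HR of 0.7 is tied to "assuming a median OS of 70 months for cabozantinib/vandetanib and 100 months for selpercatinib".

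Both sections specify a stratified log-rank test and a stratified Cox HR for OS. SAP 8.1 sets all confidence intervals at a two-sided 95% level. Neither document gives a detriment margin or an upper confidence bound for OS, or the chance of an observed HR below 1.0 when the true HR is 1.0 or more. Nothing links the OS confidence interval to the reading of detriment.

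**The concern.** The only operating characteristic given is the chance of a favourable point estimate when the drug prolongs survival. A statement of no detriment has to be judged the other way round: how often would it be made if the drug had no effect on survival, or shortened it? A point estimate below 1.0 carries no information about its own precision, and with about 125 deaths the interval around it is wide.

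At stake is what the trial may say about OS harm. As worded, both governing documents would support describing an HR just under 1.0 as no detriment while the data remained compatible with a material increase in the hazard of death. Crossover of control patients to selpercatinib after progression confirmed by blinded independent central review (BICR) (Protocol 4.2 and 5.2.1) may pull the OS HR towards 1, which would make a point estimate near 1 less informative still.

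**Working it through.** **Inputs from the documents.** 125 deaths and a true HR of 0.7 (Protocol 9.4.3.2.3, SAP 8.4.2); 2:1 allocation (Protocol 4.1); median OS of 70 months on control and 100 on selpercatinib (Protocol 9.4.3.2.3); 250 patients, rising to about 400 at most (Protocol 9.2); cap at 6 years, or 72 months.

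**Assumed, because the documents do not state it.** Exponential survival, uniform accrual over A = 24 to 48 months, no dropout.

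**Formula.** ln(observed HR) is approximately normal with mean ln(true HR) and SE = 1/√(d·p·(1−p)), where d is the number of deaths and p the fraction allocated to selpercatinib. Then P(observed HR < 1) = Φ(−ln(true HR)/SE).

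**1. The plan's own figure.** At a true HR of 0.7, −ln(0.7) = 0.3567.
- 1:1 information: SE = 1/√(125 × 1/4) = 0.1789; P = Φ(1.994) = 97.7%.
- The trial's 2:1 allocation: SE = 1/√(125 × 2/9) = 0.1897; P = Φ(1.880) = 97.0%.

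Both agree with the stated figure of about 98%.

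**2. The same outcome at other true HRs** (125 deaths, 2:1, SE = 0.1897).

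| True HR | P(observed HR < 1) |
|---|---|
| 0.7 | 97.0% |
| 1.0 | 50.0% |
| 1.1 | 30.8% |
| 1.2 | 16.8% |
| 1.3 | 8.3% |

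The 50% at a true HR of 1.0 holds for any number of deaths.

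**3. What an observed HR just below 1 leaves open.** Upper 95% limit for an observed 0.99: 0.99 × exp(1.96 × 0.1897) = 0.99 × 1.4505 = 1.44.

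**4. Deaths by the 6-year cap.** With λ = ln 2/median, the expected proportion dead in an arm is 1 − [exp(−λ(72−A)) − exp(−72λ)]/(λA). For A = 36 and 250 patients:
- selpercatinib: λ = 0.00693, proportion 0.310, 166.7 patients, 51.7 deaths;
- control: λ = 0.00990, proportion 0.411, 83.3 patients, 34.3 deaths;
- total: 86.0.

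| Accrual (months) | 250 patients | 400 patients |
|---|---|---|
| 24 | 93.8 | 150.1 |
| 36 | 86.0 | 137.6 |
| 48 | 77.7 | 124.2 |

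**5. Effect of 86 deaths.** SE = 1/√(86 × 2/9) = 0.2287. At a true HR of 0.7, P = Φ(0.3567/0.2287) = Φ(1.559) = 94%. Upper 95% limit for an observed 0.99: 0.99 × exp(1.96 × 0.2287) = 1.55.

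The counts in step 4 take the plan's HR of 0.7. If the drug were harmful, more deaths would accrue by the cap. With 36-month accrual, 250 patients and a 70-month control median, about 113 are expected at HR 1.2 and 117 at HR 1.3. P(observed HR < 1) is then about 18% and 9%, close to the 125-death figures.

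**The case against.** The strongest reply is that the sentence is a planning statement. It is conditional on a true HR of 0.7, and it sits in a paragraph that disclaims power for OS. No decision or alpha depends on it. Much of a proper OS analysis is already specified: a stratified log-rank test, a stratified Cox HR, and six sensitivity analyses, two of which censor crossover patients when they start selpercatinib (SAP 8.4.2). The independent data monitoring committee also reviews safety about every 6 months, after an early analysis that covers deaths (Protocol 9.5).

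Most of this stands, and it rules out several stronger readings that a reader might infer:
- *That an HR below 1.0 is a formal pass/fail criterion, or that it inflates type I error.* The protocol places OS under its key secondary heading, but the gatekept sequence in Protocol 4.1 and SAP 8.8 runs from PFS to treatment failure-free survival (TFFS) to comparative tolerability. OS is not in it, and SAP 8.4.2 lists it as supportive.
- *That the 98% is miscalculated.* It reproduces within rounding.
- *That serious harm would often yield an HR below 1.0.* The figures do not support this: 8% at a true HR of 1.3. The weakness is greatest for no effect and modest harm.
- *That 125 deaths cannot be reached.* Under the same accrual assumptions, about 124-150 are expected with 400 patients.

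What the reply does not remove is the gloss itself. It says in advance what an observed HR below 1.0 indicates, it appears in both governing documents, and no other text ties the planned confidence interval to the detriment question. Reporting an interval does not correct an inference drawn from the point estimate alone.

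**Conclusion.** The inference is wrong as written and should be changed. With 125 deaths and 2:1 allocation, an observed OS HR below 1.0 is a coin toss if selpercatinib has no effect on survival. It would still occur about 31% of the time if the hazard of death were raised by 10% and 17% if raised by 20%. An HR of 0.99 would leave increases of up to about 44% inside the 95% interval. These figures rest on the usual normal approximation for the log HR and on the documents' own event count and allocation.

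The further loss of precision under the 6-year cap is less certain. It depends on assumed accrual, no dropout and the final sample size, and it matters mainly if enrolment stays near 250. The fault is confined to interpretation: the planned OS test, the trial's error rates and the sample size are unaffected.

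**What to change.** In Protocol 9.4.3.2.3 and SAP 8.4.2:
- Delete the clause "indicating no OS detriment associated with the selpercatinib treatment".
- State that OS detriment is judged from the stratified Cox HR with its 95% CI, and that the upper limit is reported.
- Beside the probability at a true HR of 0.7, give the probability of an observed HR below 1.0 at a true HR of 1.0, both for 125 deaths and for the deaths expected by 6 years. State the accrual assumption and use 2:1 allocation.

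A longer table at true HRs of 1.1, 1.2 and 1.3 would be useful but is optional.

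The cost is wording in two sections and a less favourable OS statement. No patients, data collection or alpha are involved.

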9.4.3.3. Other Secondary Analyses

Overall response rate will be assessed for Arm A versus Arm B using a Cochran-Mantel-Haenszel test stratified by the randomization strata.

- ORR per RECIST 1.1 as assessed by BICR
- ORR per RECIST 1.1 per investigator assessment

The following secondary outcomes will be assessed for Arm A vs. Arm B using a logrank test stratified by the randomization strata. The corresponding HR between treatment arms will be estimated using a stratified Cox regression model (Cox 1972), stratified by the randomization strata. Point estimates with 95% CI, for each treatment arm will be estimated using the Kaplan-Meier method (Kaplan and Meier 1958):

- TFFS as assessed by investigator
- PFS as assessed by investigator
- DoR as assessed by investigator
- DoR as assessed by BICR
- PFS2 as assessed by investigator

Progression-free survival per investigator assessment is defined in the same manner as BICR PFS.

TFFS per investigator assessment is defined as the time from randomization to the first occurrence of documented radiographic disease progression per RECIST 1.1 as assessed by the investigator or unacceptable toxicity leading to treatment discontinuation as assessed by the investigator (regardless of a study drug-related AE meets protocol guidance for treatment discontinuation or not); or death (due to any cause).

Progression-free survival 2 (PFS2) is defined as the time from randomization to disease progression (radiographic or symptomatic progression as determined by the investigator) on the next line of treatment or death from any cause in the absence of observed disease progression. If the patient is alive at the cutoff for analysis, and disease progression has not been observed, PFS2 data will be censored on the latest date of last progression-free assessment or start of the next line of treatment.

Duration of response (DOR) is defined as the time from the date that measurement criteria for complete response (CR) or partial response (PR) (whichever is first recorded) are first met by the BICR or investigator assessment, as applicable, until the first date that disease is recurrent or documented disease progression is observed, per RECIST 1.1 criteria, or the date of death from any cause in the absence of documented disease progression or recurrence.

Overall response rate (ORR) is defined as the number of patients who achieve a best overall response (BOR) of CR or PR divided by the total number of patients randomized to each treatment arm. The ORR, with 95% CI, will be summarized for each treatment arm.

Best overall response is determined from a sequence of responses assessed. Two objective status determinations of CR before progression are required for a best response of CR. Two determinations of PR before progression, but not qualifying for a CR, are required for a best response of PR. The second objective response is required to be ≥ 28 days after the initial response.

9.4.3.4. RET-Testing Concordance Analysis

The concordance between *RET* testing results based on local laboratory tests and centrally assessed results will be evaluated. Details regarding analyses involving centrally assessed *RET*-testing results will be described in a separate Diagnostics SAP.

9.4.3.5. Tertiary/Exploratory Analyses

The following endpoints will be assessed as tertiary/exploratory analyses, with detailed methods provided in the SAP:

Time to initiation of new anticancer therapy, defined as the time from randomization to documentation in the CRF of a new local (e.g., surgery, radiation) or systemic anticancer treatment administered to the patient.

PFS after crossover, defined as the time from start of selpercatinib treatment until the occurrence of disease progression or death from any cause for crossover population.

Calcitonin and CEA response rate, defined as percentage of patients who had a decline from baseline in the calcitonin or CEA level of at least 50% maintained for at least 4 weeks.

9.4.4. Safety Analyses

Detailed tabulations of safety data (AEs and clinical laboratory tests) will be provided for all subjects receiving the study drug. The number and percent of subjects with TEAEs will be summarized. Summary of other safety parameters by treatment group will be provided where appropriate.

Safety data after crossover will be summarized for crossover population. TEAEs and clinical laboratory abnormalities will be defined according to the crossover baseline with details provided in the SAP.

9.4.5. Pharmacokinetic/Pharmacodynamic Analyses

Selpercatinib plasma concentrations will be summarized by descriptive statistics and graphics. Additionally, the data will be evaluated through population PK methodology.

The relationship between selpercatinib plasma exposure and pharmacodynamic markers, such as tumor size, efficacy, as well as selected safety outcomes, will be explored.

9.4.6. Biomarker Analysis

Biomarker results will be summarized and may be analyzed for correlations with clinical outcomes.

9.4.7. Other Analyses

9.4.7.1. Health Economics

9.4.7.1.1. Patient Reporting Outcomes (PROs)

For each instrument, percentage compliance will be calculated as the number of completed assessments divided by the number of expected assessments. Data will be separately summarized using descriptive statistics.

Further details will be provided in the SAP for each PRO instrument, respectively.

9.4.7.1.2. Healthcare Resource Utilization

Frequency counts of hospitalizations, duration of stay, emergency room visits, GCSF use, transfusions and analgesic use will be reported descriptively for each treatment arm by cycle.

9.4.7.2. Subgroup Analyses

To determine whether the treatment effect is consistent across various subgroups, the between-group treatment effect for OS, PFS, TFFS and ORR (with a nominal 95% CI) will be estimated and plotted within each category of the following subgroups (defined based on eCRF data):

- Age category (≤ 65 vs. > 65 years)
- ECOG Performance Scale (0-1 vs. 2)
- Sex (female vs. male)
- Race (Asian vs. non-Asian)
- Tissue vs. blood *RET* mutation detection
- *RET* mutation: M918T vs. other
- Investigator's choice of treatment with cabozantinib vs. vandetanib

If a level of a factor includes fewer than 5% of the ITT population, analysis within that level will be omitted. Additional subgroup analyses may be performed as deemed appropriate.

9.5. Interim Analyses

[figure not shown]
An interim analysis will be triggered after approximately 56 PFS events by BICR have occurred (at 75% information fraction). Based on the observed HR of PFS by BICR and pre-specified criteria, the study results at interim analysis will be categorized into 4 determination zones: efficacious, favorable, promising, and unfavorable.

- If the study results fall into the **efficacious** zone, a positive study will be declared due to overwhelming efficacy, enrollment will be stopped, and regulatory interactions will be initiated.

- If the study results fall into the **favorable** zone, the study will continue to the final analysis with the initially planned total number of events at 74 (i.e., no re-estimation will be conducted).
- If the study falls into the **promising** zone, the total number of events will be increased. The events re-estimation will be based on the observed PFS HR according to the method provided in Cui et al. (1999). The total number of patients will be increased and determined accordingly so that the required number of events could be achieved in a desired timeframe.
- If the study results fall into the **unfavorable** zone, enrollment will be halted, and the study will continue to the final analysis.

The criteria for each zone will be prespecified in the Adaptive Design Charter.

The figure below provides an overview of the proposed adaptive design. At the pre-specified interim efficacy analysis, the sample size/total number of events for the final analysis will be determined. If the study is not declared positive, final analysis will be conducted according to a determination zone (favorable, promising, or unfavorable), based on where the interim results fall. At final analysis, the study will be declared positive if the critical boundary is met. To preserve the type I error, the Rho family alpha spending function (Kim and DeMets 1987) will be used to account of multiple analyses, and a weighted test statistic proposed in the CHW method will be used as the primary test at final analysis. All significance levels and weights in CHW method will be based on the actual number of events observed at the time of analyses.

An independent Data Monitoring Committee (IDMC) will be established to conduct interim efficacy and safety analyses and will follow an approved IDMC charter. The IDMC may initiate a consultation with an appropriate expert (such as cardiac) if additional expertise is needed regarding evaluation of any safety signals. The IDMC will communicate back to a Lilly Senior Management Designee (SMD) about their assessment.

An early safety analysis will be performed after approximately 50 subjects have been randomized and had the opportunity to be treated for 2 cycles. This analysis will focus on deaths, treatment discontinuations, SAEs, and Grade 3/4 AEs. The IDMC will meet and review data

approximately every 6 months thereafter. Detailed information on the role of the IDMC and frequency of meetings will be provided in the IDMC charter separate from this protocol.

For interim efficacy analysis and the sample size re-estimation, the IDMC will be provided with pre-specified decision rules as described in the Adaptive Design Charter. The SAC will be responsible for preparing and reporting interim efficacy analysis results to the IDMC. This practice will ensure that Lilly personnel involved in the day-to-day management and conduct of the trial do not have access to unblinded comparative results, even inadvertently. The IDMC will review unblinded results and make a recommendation on declaring the study positive for overwhelming efficacy or continuing the study with a certain total number of events according to the plan. IDMC recommendations will exclude any details of the interim efficacy analysis results.

Following the determination of the required number of events for the final analysis by the IDMC, Lilly study team will confirm the total number of patients in order to ensure achievement of the required number of events for the final analysis. This determination will be made in a blinded manner using the pooled PFS data.

10. Supporting Documentation and Operational Considerations

